6.6 Permitted Concomitant Medications and Procedures

Restricted use of H₂-receptor antagonists or neutralizing antacids is permitted after completion of the required PK/ECG assessments on Cycle 1, Day 3, for patients continuing to receive treatment with MLN0128, under the following conditions:

- Treatment with H₂-receptor antagonist is not permitted less than 24 hours before and within 6 hours after receiving a dose of MLN0128. Examples of H₂-receptor antagonist include: ranitidine, cimetidine, and nizatidine.
- Treatment with neutralizing antacids is not permitted less than 4 hours before and within 6 hours after receiving a dose of MLN0128.

Other medications considered necessary for the safety and well-being of the patient may be administered at the discretion of the investigator. Any concomitant medications added or discontinued during the study should be recorded on the electronic case report form (eCRF).

6.7 Precautions and Restrictions

Dietary restrictions include periods of fasting as described in Section 7.4.16, and in-home daily fasting glucose monitoring (refer to Section 7.4.18).

Patients who show evidence of hyperglycemia during the study should be encouraged to follow a low-carbohydrate diet.

It is not known what effects MLN0128 has on human pregnancy or development of the embryo or fetus. Therefore, female patients participating in this study should avoid becoming pregnant, and male patients should avoid impregnating a female partner. Non-sterilized female patients of reproductive age group and male patients should use effective methods of contraception through defined periods during and after study treatment as specified below.

Female patients must meet 1 of the following:

- Postmenopausal for at least 1 year before the screening visit, or

- Surgically sterile, or
- If they are of childbearing potential, agree to practice 2 effective methods of contraception from the time of signing of the informed consent form through 3 months after the last dose of study drug, or
- Agree to practice true abstinence, when this is in line with the preferred and usual lifestyle of the subject. (Periodic abstinence [eg, calendar, ovulation, symptothermal, postovulation methods] and withdrawal are not acceptable methods of contraception.)

Male patients, even if surgically sterilized (ie, status postvasectomy) must agree to 1 of the following:

- Practice effective barrier contraception during the entire study treatment period and through 3 months after the last dose of study drug, or
- Agree to practice true abstinence, when this is in line with the preferred and usual lifestyle of the subject. (Periodic abstinence [eg, calendar, ovulation, symptothermal, postovulation methods for the female partner] and withdrawal are not acceptable methods of contraception.)

6.8 Management of Clinical Events

6.8.1 Management of Nausea and/or Vomiting

This study will employ prophylactic anti-emetic on Cycle 1, Day 1.

For patients remaining in the study after completing the required PK/ECG assessment period (Cycle 1, Day 3), guidance for the management of nausea and/or vomiting is provided in [Table 6-2](#).

MLN0128
Clinical Study Protocol C31002 Protocol Amendment 2

Table 6-2 Management of Nausea and/or Vomiting

Grade	Description	Treatment	MLN0128 Dose Modification
≤ 2	Loss of appetite with or without decreased oral intake; 1-5 episodes of vomiting within 24 hours	Maximize anti-emetic therapy; consider IV fluid hydration	None
≥ 3	Inadequate oral intake; ≥ 6 episodes of vomiting within 24 hours	Maximize anti-emetic therapy; initiate tube feeding, IVF, or TPN	Hold until ≤ Grade 1; resume MLN0128 without dose modification

Prevention/Prophylaxis

Prophylactic use of anti-emetic, antinausea, and antidiarrheal medications is encouraged, and these may be administered before each dose of MLN0128 as needed throughout the study.

Abbreviations: IV = intravenous; IVF = intravenous fluids; TPN = total parenteral nutrition.

6.8.2 Management of Hyperglycemia

In addition to obtaining fasting glucose levels at the clinic visits as outlined in the [Schedule of Events](#), all patients will be provided with a glucometer and trained to use it to monitor their daily predose FBG levels at home. Patients will be instructed to notify the study staff immediately of any abnormal readings (ie, ≥ 150 mg/dL) for further instructions on the management of their hyperglycemia. Hyperglycemia observed during home glucose monitoring should be confirmed in the clinic. Investigators will be responsible for reviewing the home glucose monitoring logs for hyperglycemia. If no irregularities in the FBG level are observed during a minimum of 6 consecutive months, then the frequency of in-home fasting glucose testing may be reduced to twice weekly if the investigator approves. Patients will continue to notify the investigator of FBG levels ≥ 150 mg/dL, and if blood glucose levels are not well controlled, or if they require either oral hypoglycemic agents or insulin to control blood glucose levels, then the frequency of in-home testing of FBG levels will be reinstated to daily. Guidelines for management of hyperglycemia are presented in [Table 6-3](#).

MLN0128
Clinical Study Protocol C31002 Protocol Amendment 2

Table 6-3 Management of Hyperglycemia

Grade	Description	Treatment	MLN0128 Dose Modification
1	FBG > ULN– 160 mg/dL	Continue close monitoring of blood glucose. Initiate oral hypoglycemic agent.	None
2	FBG > 160– 250 mg/dL	Initiate oral hypoglycemic agent and/or insulin if not well controlled on oral agent.	None
≥ 3	FBG > 250 mg/dL	Initiate oral hypoglycemic agent and/or insulin.	Hold drug until ≤ Grade 2. Resume MLN0128 based on timing of recovery: 
 • ≤ 1 week: resume at same dose and schedule • > 1 but ≤ 2 weeks: reduce by 20% • 2 weeks: stop MLN0128 and discontinue patient from the study

Prevention/Prophylaxis

- Follow fasting glucose levels during clinic visits.
- Monitor home glucometer test results.
- Check HbA1c levels every 3 months during therapy.
- Recommend lifestyle modifications, as appropriate (balanced diet, limited alcohol consumption, increased physical activity).
- Most episodes of Grade 1 and 2 hyperglycemia respond quickly to oral metformin. Early initiation of therapy is recommended to prevent higher grade hyperglycemia.
- FBG levels ≥ 150 mg/dL by glucometer should be followed by closer monitoring of serum glucose and possible intervention.

Abbreviations: FBG = fasting blood glucose; HbA1c = glycosylated hemoglobin; ULN = upper limit of the normal range.

If any fasting glucose reading performed at the site indicates hyperglycemia (fasting glucose > ULN or ≥ 110 mg/dL), the study staff should first confirm that the patient was fasting at the time of the blood draw (ie, nothing by mouth for at least 8 hours before). To aggressively manage the hyperglycemia per standard clinical practice, the following guidelines are provided to aid the investigator in initiating antiglycemic therapies.

Based on the clinical experience in MLN0128 trials, most episodes of hyperglycemia observed have been Grade 1 or Grade 2 and have responded quickly to oral metformin. Hyperglycemia has not been dose-limiting since instituting a standard regimen for early treatment of hyperglycemia. All patients developing hyperglycemia on the study should have their glucose closely monitored by study staff. The investigator may choose either to continue close monitoring of patients who develop Grade 1 hyperglycemia (fasting glucose > ULN ≤ 160 mg/dL) or consider initiating treatment with an oral hypoglycemic agent, such

MLN0128**Clinical Study Protocol C31002 Protocol Amendment 2**

as metformin. All patients with \geq Grade 2 hyperglycemia (fasting glucose > 160 mg/dL) must be treated aggressively with oral hypoglycemic agents and/or insulin as clinically indicated while continuing on MLN0128 treatment. The investigator should consult an endocrinologist if needed to aid in optimizing the hyperglycemia treatment plan of the patient.

It is recommended that patients be treated initially with a fast-acting insulin sensitizer, such as metformin at 500 mg orally QD, and titrate up to a maximum of 1000 mg orally twice daily as needed. Concurrent addition to metformin of dipeptidyl peptidase-4 inhibitors (eg, sitagliptin or vildagliptin) and/or insulin should also be considered. Oral sulfonylureas (eg, glipizide or glyburide) should be used with caution due to the higher risk of inducing hypoglycemia in patients. The dose of oral hypoglycemic agents should be adjusted in patients with renal insufficiency.

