6.4 Dose-Modification Guidelines

MLN0128 is administered QW in continuous cycles of 28 days. Study drug should be administered continuously unless a \geq Grade 3 MLN0128-related event occurs.

For management of toxicity for individual patients, dose adjustments may include interruption of treatment with study drug and a dose reduction. If continued treatment with MLN0128 is thought to be beneficial by the investigator, and with the sponsor's approval, dose reductions should be based on the guidelines provided below and in [Table 6-1](#).

Patients whose dose is reduced will not be allowed to re-escalate.

Dosing should be interrupted for \geq Grade 3 MLN0128-related toxicities. If the event resolves to Grade 1 or baseline values within 14 days of interrupting treatment, depending on the severity of the toxicities, the patient may resume study drug as follows:

- Resume study treatment at 30 mg QW dose, or

MLN0128**Clinical Study Protocol C31002 Protocol Amendment 2**

- Resume study treatment at 20 mg QW (33% reduction)

If the toxicity recurs at the 20 mg QW dose, dosing should be interrupted. If the event resolves to Grade 1 or baseline values within 14 days of interrupting treatment, depending on the severity of the toxicity, the patient may resume study drug as follows:

- Resume study treatment at 20 mg QW, or
- Resume study treatment at 15 mg QW (25% dose reduction)

The sponsor's project clinician should be contacted before any dose modification of MLN0128 for any patient in the study.

Table 6-1 Dose Reduction Schedule for MLN0128

Dose Level	Percent Reduction	Dose
0	0%	30 mg QW
-1	33%	20 mg QW
-2	25%	15 mg QW

Abbreviation: QW = once weekly.

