6.4.4 Criteria for Discontinuation

Grade 4 nonhematologic toxicities will in general require that treatment with MLN0128 be permanently discontinued. If, in the opinion of the investigator and the project clinician, it is in the best interest of the patient to continue treatment with MLN0128, then the dose of

MLN0128**Clinical Study Protocol C31002 Protocol Amendment 2**

MLN0128 should be reduced by at least 1 dose level after recovery of the toxicity and/or intolerance to Grade 1 or to baseline values.

If dosing is delayed for > 14 consecutive days for MLN0128-related toxicities despite supportive treatment per standard clinical practice, or more than 2 dose reductions of MLN0128 are required for a patient, treatment should be stopped, the patient discontinued from the study, and the follow-up visit completed within 30 days of the last dose of MLN0128.

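### The 20% reduction in one row each of Tables 6-3 to 6-6 gives doses that 5 mg capsules cannot make up and that are not on the Table 6-1 schedule

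*Protocol*

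**What the plan says.** Protocol Section 6.4 states that "dose reductions should be based on the guidelines provided below and in" Table 6-1. That table has three levels: 30 mg QW (level 0), 20 mg QW (level -1, a 33% cut) and 15 mg QW (level -2, a 25% cut). Dosing is interrupted at or above "Grade 3 MLN0128-related toxicities. If the event resolves to Grade 1 or baseline values within 14 days of interrupting treatment", and the two options on recovery are "Resume study treatment at 30 mg QW dose, or" and "Resume study treatment at 20 mg QW (33% reduction".

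Four event-specific tables in Section 6.8 give a different size of reduction, in one row each:

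- Table 6-3, hyperglycemia, Grade 3 or higher: "> 1 but ≤ 2 weeks: reduce by 20" (percent).
- Table 6-4, hyperlipidemia, Grade 3: restart 20% lower after recovery.
- Table 6-5, oral mucositis, Grade 3: the same.
- Table 6-6, rash, Grade 3 or higher: 20% lower if recovery takes 2 weeks or less.

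Section 6.1 supplies MLN0128 only as 5 mg capsules, to be swallowed whole and not opened or manipulated. No rounding rule is given, and nothing maps 20% to a Table 6-1 level.

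**The concern.** A dose-modification rule should lead to a dose the site can hand out. These four rows do not, if the patient is on a Table 6-1 level. A site that follows the row literally needs a fraction of a capsule. A site that rounds must choose between the nearest whole-capsule dose and the scheduled level, and from 30 mg these differ. Patients with the same Grade 3 event could then continue on different doses.

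A knock-on effect is possible because reductions are capped. Section 6.4.4 says that if "more than 2 dose reductions of MLN0128 are required for a patient, treatment should be stopped". A patient taken from 30 to 25 mg and then, by another 20% cut, to 20 mg would have used both reductions without reaching 15 mg. A patient on the schedule would have reached 15 mg with the same two. This matters only if a 25 mg dose is approved.

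At stake is consistent toxicity management for patients who stay on treatment, which can last up to 12 months or longer by agreement. The QT assessment is complete before any of this applies.

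**Working it through.** **Inputs.** Levels of 30, 20 and 15 mg QW (Table 6-1); a 20% reduction (Tables 6-3 to 6-6); a 5 mg capsule taken whole (Section 6.1); once-weekly dosing in 28-day cycles, so 4 doses per cycle (Section 6.4).

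**Step 1: reproduce Table 6-1.** Percent cut = (old dose − new dose) / old dose.

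- 30 to 20 mg: (30 − 20)/30 = 33.3%.
- 20 to 15 mg: (20 − 15)/20 = 25.0%.

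Both agree with the table, each percentage being relative to the level above. Neither is 20%.

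**Step 2: apply the 20% rule.** New dose = 0.80 × current dose; capsules = new dose / 5.

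| Current dose | After 20% cut | Capsules | Whole number? | Table 6-1 level? |
|---|---|---|---|---|
| 30 mg | 24 mg | 4.8 | no | no |
| 20 mg | 16 mg | 3.2 | no | no |
| 15 mg | 12 mg | 2.4 | no | no |

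**Step 3: which rows matter in practice.**

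- From 30 mg, the whole-capsule doses either side of 24 mg are 25 and 20 mg. 25 mg is 1 mg away, a cut of (30 − 25)/30 = 16.7%, and is off the schedule. 20 mg is 4 mg away, a cut of 33.3%, and is level -1. Per cycle this is 4 × 25 = 100 mg against 4 × 20 = 80 mg.
- From 20 mg, the nearest whole-capsule dose to 16 mg is 15 mg, which is level -2. Rounding and the schedule agree, so little doubt remains.
- From 15 mg, a patient who came down by two reductions would stop under Section 6.4.4, so 12 mg is largely theoretical.

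**Step 4: check for a starting dose at which 20% works.** Section 4.1 allows continuation at up to 30 mg, while Section 6.1 gives 30 mg. If 25 mg were used, 0.80 × 25 = 20 mg, or 4 capsules. The capsule problem is therefore specific to the Table 6-1 levels; 25 mg is not one of them.

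**The case against.** The strongest reply is that the protocol already points to Table 6-1. The sentence in Section 6.4 that bases reductions on the table also requires the sponsor's approval. In addition, the sponsor's "project clinician should be contacted before any dose modification of MLN0128 for any patient in the study". Section 6.4.1 sends any dose-limiting toxicity after Cycle 1, Day 3 to Section 6.4 for interruption and reduction. Sections 6.4.2 and 6.4.3 point there too, and the Section 6.8 tables are introduced only as guidance or guidelines. On this view a 25 mg dose would arise only if the sponsor approved a dose off its own schedule, while 20 mg is dispensable, scheduled and at least a 20% cut.

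Most of this stands. A reader might infer that nothing in the protocol indicates which rule governs. The documents do not support that: for the size of a reduction, the text leans towards Table 6-1. Under Section 6.3, related Grade 3 mucositis or hyperlipidemia despite adequate treatment, and such Grade 3 rash lasting more than 3 days, can be dose-limiting and so go to Section 6.4.

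Two things survive. The dose-limiting route does not cover everything: Section 6.3 excepts Grade 3 hyperglycemia lasting 14 days or less, which is the Grade 3 case that the Table 6-3 row addresses, and Grade 3 rash lasting 3 days or less. Also, leaning towards Table 6-1 does not make 24 mg dispensable. The rows still state a reduction that cannot be carried out from any scheduled level, and the clinician contact supplies no rounding rule.

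**Conclusion.** The point holds as a wording error of limited reach. Four rows, one in each of four tables, direct a reduction that cannot be given from 30, 20 or 15 mg and does not match the schedule in Section 6.4. The practical doubt is mainly one step, from 30 mg to either 25 or 20 mg, or 20 mg of drug per four-dose cycle (100 − 80). This assumes that patients continue at 30 mg, as Section 6.1 states, and that only the 5 mg strength is available.

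The primary QTcI endpoint, the single 40 mg dose and Cycle 1 pharmacokinetic sampling are not affected, since all are complete by Cycle 1, Day 3.

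A reader might also take other differences between Sections 6.4 and 6.8 as errors of the same kind. Tables 6-3 and 6-6 accept recovery to Grade 2 where Section 6.4 asks for Grade 1 or baseline. Section 6.4 lets the patient resume at 30 or 20 mg. Table 6-2 directs no reduction. The documents do not show these to be mistakes: they may be intended event-specific rules, and Section 6.4 makes its choice depend on severity. Which recovery grade applies, and whether to reduce at all, is a separate clinical choice for the sponsor.

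**What to change.** In the four rows of Tables 6-3, 6-4, 6-5 and 6-6, replace *reduce by 20%*, *20% dose reduction* and *reduce dose by 20%* with *reduce by 1 dose level (Table 6-1)*. Section 6.4.4 already speaks of reducing by dose level, so the term is not new to the protocol.

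The first cut is then 30 to 20 mg (4 capsules) and the second 20 to 15 mg (3 capsules); a need for a third falls under Section 6.4.4, as now. That section's provision that "Grade 4 nonhematologic toxicities will in general require that treatment with MLN0128 be permanently discontinued" is also unaffected.

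The cost is four phrases, with no change to data collection or analysis. The downside is that the first cut becomes 33% instead of a nominal 20%, but that is the step Table 6-1 already sets. If the sponsor wants a gentler first step, the place to make it is Table 6-1, by adding a level that is a whole number of capsules.

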6.4.1 Criteria for Beginning or Delaying a Subsequent Treatment Cycle

MLN0128 is administered in continuous cycles; therefore, study drug should be administered continuously unless a \geq Grade 3 MLN0128-related event occurs. Patients who experience an AE meeting the definition for a DLT after Cycle 1, Day 3 should have their study drug treatment interrupted and reduced as outlined in Section 6.4.

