6.4.2 Criteria for Dose Interruption During a Cycle

See Section 6.4 for dose modification guidelines.

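### Protocol Section 6.8.2 has all Grade 2 or higher hyperglycemia treated with MLN0128 continuing and sets no upper limit; read literally, this conflicts with the dose hold above 250 mg/dL

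*Protocol*

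**What the plan says.** Protocol Section 6.8.2 gives its hyperglycemia rules twice. Before the table it says "Guidelines for management of hyperglycemia are presented in" Table 6-3. That table has a dose-modification column: no change at Grade 2 (> 160 to 250 mg/dL), and at Grade 3 or higher (> 250 mg/dL) "Hold drug until ≤ Grade 2. Resume MLN0128 based on timing of recovery". A patient who recovers within 1 week resumes the same dose. Recovery after more than 1 and up to 2 weeks brings a 20% reduction, and the last step is to stop drug and take the patient off study.

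The text after the table covers Grade 1, then all patients at Grade 2 or higher (fasting glucose > 160 mg/dL), who "must be treated aggressively with oral hypoglycemic agents and/or insulin as clinically indicated while continuing on MLN0128 treatment".

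The general rules are in Section 6.4:

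- Section 6.4: "Dosing should be interrupted for \geq Grade 3 MLN0128-related toxicities".
- Section 6.4.1: "study drug should be administered continuously unless a \geq Grade 3 MLN0128-related event occurs".
- Sections 6.4.2 and 6.4.3 refer back: "See Section 6.4 for dose modification guidelines".
- Section 6.4.4: "Grade 4 nonhematologic toxicities will in general require that treatment with MLN0128 be permanently discontinued". If the investigator and project clinician agree to go on, the dose of "MLN0128 should be reduced by at least 1 dose level after recovery of the toxicity".

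**The concern.** The sentence sets a floor of 160 mg/dL and no ceiling, so its own wording takes in Grades 3 and 4. In that range it has the patient stay on a drug that the dosing rules withhold. Its verb is also the firmest of the set: Section 6.4 says only that dosing should be interrupted, and Table 6-3 is introduced as guidelines. Nothing in the protocol says that the table overrides the text.

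The stake is dosing safety, and the literal reading errs in the less safe direction. Hyperglycemia is a recognized effect of MLN0128 (Protocol Section 1.2) and an adverse event of interest in SAP Section 5.10.1.1. Patients enter without diabetes and with fasting glucose of at most 120 mg/dL, so a value above 250 mg/dL is more than twice the entry limit (250/120 = 2.08). About 6 centers will apply the rule and could apply it differently.

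**Working it through.** The plan states no figure to reproduce here. The check sets the instructions side by side by grade and then sizes one affected dose.

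**Step 1. Action on MLN0128 by grade**

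| Grade (fasting glucose) | 6.8.2 text, read literally | Table 6-3 | 6.4 and 6.4.1 | 6.4.4 | Agree? |
|---|---|---|---|---|---|
| 2 (> 160 to 250 mg/dL) | continue | no modification | no interruption | not applicable | yes |
| 3 (> 250 mg/dL) | continue | hold | interrupt, if MLN0128-related | not applicable | no |
| 4 (> 250 mg/dL; no separate cut-off given) | continue | hold | interrupt, if MLN0128-related | in general stop for good; otherwise at least one level down after recovery | no |

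The conflict with Table 6-3 is the firmest, because the table does not ask whether the event is drug-related. Sections 6.4 and 6.4.1 do, so they conflict with the sentence only for MLN0128-related events. The Grade 4 conflict rests on the grade alone, since the documents give no glucose value separating Grade 4 from Grade 3.

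**Step 2. Does another rule lift the hold?** Section 6.3 exempts Grade 3 hyperglycemia lasting up to 14 days from the definition of dose-limiting toxicity. That does not help: the hold in Table 6-3 and the interruption in Section 6.4 turn on grade, not on whether the event is dose-limiting.

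**Step 3. Size for one weekly dose due while glucose is above 250 mg/dL.** Dose levels are those of Table 6-1.

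| Level | Sentence, literally | Hold | Difference |
|---|---|---|---|
| 0 | 30 mg | 0 mg | 30 mg |
| -1 | 20 mg | 0 mg | 20 mg |
| -2 | 15 mg | 0 mg | 15 mg |

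This is simply a dose given against a dose held. The number of such doses cannot be estimated: the documents give no rate, onset or duration for Grade 3 or higher hyperglycemia, and Section 4.3 lets treatment run past 12 months.

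**Step 4. What a repair must also settle at Grade 4.** The Table 6-3 row covers Grade 3 or higher without separating the two. Take a patient on 30 mg with Grade 4 hyperglycemia who recovers within 1 week. Table 6-3 resumes 30 mg. Section 6.4.4 gives 0 mg (permanent discontinuation) or, by agreement, at most 20 mg (one level down). Correcting the sentence alone would leave these two resumption rules in place.

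**The case against.** The strongest reply is that continuing treatment need not mean that no dose is missed. Section 6.4 speaks of continued treatment when introducing rules that include interruption and reduction. Section 6.4.4 speaks of continuing treatment for a patient whose dose is reduced after recovery. In both places the phrase means not stopping for good. On that reading the sentence tells sites to treat the glucose and keep the patient on the program, and Table 6-3 says which doses to hold. The obligation also attaches to treating the glucose; continuing drug is a subordinate phrase in a paragraph introduced as help with starting glucose-lowering therapy. With weekly dosing, a site usually has time to consult the table.

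Much of this stands. The softer reading is available, and the hold is clearly intended: Table 6-3 is the named guideline, and Sections 6.4.2 and 6.4.3 send interruption and reduction to Section 6.4. But usage is not uniform, since Section 6.4 also refers to interrupting treatment, so the phrase is ambiguous and not harmless. Nor does the softer reading remove every conflict. Table 6-3 stops drug altogether when recovery is too slow, and Section 6.4.4 generally ends treatment at Grade 4.

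A reader might infer that the protocol deliberately exempts hyperglycemia from the hold, because Section 6.8.2 also says it has not been dose-limiting since early treatment became standard. The documents do not support that: the hold appears in the same section's own table.

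**Conclusion.** The point holds as an ambiguity that is potentially unsafe if followed literally. The sentence agrees with the dosing rules at Grade 2. Above 250 mg/dL its literal wording conflicts with Table 6-3 without condition, with Sections 6.4 and 6.4.1 for MLN0128-related events, and at Grade 4 with the general rule in Section 6.4.4. The size is one full dose (30, 20 or 15 mg against 0 mg) for each weekly dose due in that range.

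Three stronger conclusions are not supported:

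- **That many patients will be dosed through severe hyperglycemia.** No rate for Grade 3 or higher is given. Section 6.8.2 says most episodes were Grade 1 or 2, so few patients are likely to be affected.
- **That Sections 6.4 and 6.4.1 are contradicted in every case.** They apply only to MLN0128-related events.
- **That the primary result is at risk.** The primary endpoint is the change in QTcI on Cycle 1, Day 1 after the single 40 mg dose; the issue arises only with later weekly doses in the optional continuation phase.

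A correction should be made because the instruction concerns safety and the repair costs almost nothing.

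**What to change.** Make three edits in the next protocol amendment.

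1. In Section 6.8.2, limit the sentence to Grade 2, with fasting glucose > 160 to 250 mg/dL. Its treatment requirement and the continuation of MLN0128 can stay as they are for that grade.
2. Directly after it, add: *For Grade 3 or higher (> 250 mg/dL), treat and hold MLN0128 per Table 6-3; for Grade 4, Section 6.4.4 takes precedence over the Table 6-3 resumption schedule.*
3. Add the same Grade 4 note to the Table 6-3 row for Grade 3 or higher, so that text and table give one resumption rule.

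The text and the table would then agree on the hold at every grade, and Grade 4 would have one rule for resuming. The edits do not reconcile the recovery thresholds for resuming after Grade 3 (Grade 2 or lower in Table 6-3, Grade 1 or baseline in Section 6.4), which are a separate matter.

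The cost is one sentence edited, one sentence added, one table note and a clarification letter to sites. No extra data, patients or analyses are needed.
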